 - b) Platelet response (HI-P):
 - Major response: For patients with a pretreatment platelet count less than $100 \times 10^9/L$, an absolute increase of $30 \times 10^9/L$ or more; for platelet transfusion-dependent patients, stabilization of platelet transfusion independence.
 - Minor response: For patients with a pretreatment platelet count less than $100 \times 10^9/L$, a 50% or more increase in platelet count with a net increase greater than $10 \times 10^9/L$ but less than $30 \times 10^9/L$.
 - c) Neutrophil response (HI-N):
 - Major response: For absolute neutrophil count less than $1.5 \times 10^9/L$ before therapy, at least a 100% increase, or an absolute increase of more than $0.5 \times 10^9/L$, whichever is greater.
 - Minor response: For ANC less than $1.5 \times 10^9/L$ before therapy, ANC increase of at least 100%, but absolute increase less than $0.5 \times 10^9/L$.

10. Exploratory Studies

The baseline expression of CD38 in leukemic blasts will be assessed by flow cytometry. Expression of other marker of leukemia blasts will be available as part of routine clinical flow cytometry. This will include but not limited to CD33, 34 etc.

The mutation profile of leukemia relevant genes also will be available as part of routine work up done through Molecular Diagnostic Laboratory at MDACC.

11. Statistical Considerations

This is a Phase II study of daratumumab and venetoclax in patients with relapsed/refractory AML, high risk MDS and T-ALL/T-LBL. Subjects will be enrolled in a cohort size of 6 with up to 36 to receive daratumumab and Venetoclax. The intent will be to enroll at least 10 patients with T-ALL. Daratumumab will be administered at a starting dose of 16mg/kg every week for 8 weeks (2 cycles), followed by 16mg/kg every 2 weeks for 16 weeks (4 cycles), and then every 4 weeks until progression or up to 1 year of treatment, whichever comes earlier. Venetoclax administration will follow its package insert dosing guidelines for AML. The primary endpoint of this study is overall response (OR), defined as achievement of complete remission (CR), CR with incomplete platelet recovery (CRp), partial remission (PR), morphologic leukemia-free

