state or marrow CR within 12 weeks of treatment. The method of Thall, Simon and Estey[26] will be used to monitor efficacy and safety. The design software Multc Lean Desktop (version 2.1) developed by the Department of Biostatistics at M. D. Anderson Cancer Center (MDACC) was used to generate the stopping boundaries and the operating characteristics table for futility and toxicity monitoring.

Futility

We assume a target response rate of 25% and a response rate of 15% or lower will be considered not desirable. The study will be stopped early if the data suggest that:

$$\Pr(P_E > P_H + 0.10 | \text{data}) < 0.025$$

where P_E and P_H are the response rates for daratumumab in combination with venetoclax and historical treatment, respectively. That is, if at any time during the study we determine that there is less than 2.5% chance that the response rate improves over historical rate by more than 10%, the trial will be stopped due to futility. P_E and P_H are assumed to follow a prior of Beta (0.3, 1.7) and Beta (150, 850), respectively. The stopping boundaries for efficacy based on these assumptions and monitoring conditions are provided in **Table 4**. We will apply these stopping boundaries in cohort sizes of 6.

Table 4. Stopping boundaries for futility monitoring

# of patients evaluated for response	Stop the trial if # of patients with response is less than or equal to:
6-12	0
18	0-1
24	0-2
30	0-3
36	0-4

Toxicity

Unacceptable toxicities are defined as any treatment-related grade 3 or higher non-hematologic toxicities that occur within the first 12 weeks of treatment. Denote the probability of toxicity by P_T . We assume as a priori, $P_T \sim \text{beta}(0.6, 1.4)$. Our stopping rule is given by the following probability statement:

$$\Pr(P_T > 0.30 | \text{data}) > 0.975.$$

That is, we will stop the trial for new patient enrollment if at any time during the study, we determine that there is more than 97.5% chance that the unacceptable toxicity rate is more than 30%. This toxicity monitoring rule will be applied after the first 6 patients have been enrolled and evaluated, and then in cohort size of 6. Stopping boundaries corresponding to this stopping rule are listed in **Table 5**. The operating characteristics for efficacy and toxicity monitoring are summarized in **Table 6**.

Table 5. Early stopping boundaries for toxicity monitoring

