# of patients (in cohort size of 6, starting from the 6 th patient)	Stop the trial if there are this many patients with toxicities:
6	5-6
12	8-12
18	10-18
24	13-24
30	15-30
36	17-36

Table 6. Operating characteristics for efficacy and toxicity monitoring

True response rate	True toxicity rate	Prob (stop the trial early)	Average number of patients treated
0.15	0.10	0.5752	25.3
	0.30	0.5959	24.7
	0.40	0.7049	22.3
	0.50	0.8895	17.3
0.25	0.10	0.2119	35.0
	0.30	0.2504	34.1
	0.40	0.4526	30.2
	0.50	0.7950	22.3
0.30	0.10	0.1282	37.6
	0.30	0.1708	36.6
	0.40	0.3945	32.3
	0.50	0.7732	23.6

Analysis Plan

Summary statistics will be provided for continuous variables and frequency tables will be used to summarize categorical variables. We will estimate the overall response rate, along with the Bayesian 95% credible interval. Kaplan-Meier method will be used to estimate overall survival, time to treatment and progression-free survival. The two-sided log-rank tests will be used to assess the differences of time-to-event outcomes between subgroups of patients. Logistic regression analyses will be used to explore the association between biomarker and response or resistance to therapy.

Data from all subjects who receive any study drug will be included in the safety analyses. Subjects who entered the study but did not take any of the study drug and had this confirmed will not be evaluated for safety. The severity of the toxicities will be graded according to the NCI CTCAE v4.03 whenever possible. We will follow standard reporting guidelines for adverse events. Safety data will be summarized by category, severity and frequency.

12. Adverse Events and Reporting Requirements

Adverse event reporting will be as per the current NCI criteria and the Leukemia-specific Adverse Event Recording and Reporting Guidelines (Appendix D) . The descriptions and grading scales found in the revised NCI Common Terminology Criteria for Adverse Events (CTCAE) version 4.03 will be utilized for adverse event reporting.

<http://ctep.cancer.gov/reporting/ctc.html>

A. Adverse Events

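### Neither the futility rule nor the final response rate has a defined denominator, and Table 6's stopping probabilities hold only if every treated patient counts

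*Combined protocol and SAP*

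**What the plan says.** Section 11 (Statistical Considerations) defines the primary endpoint as CR, CRp, PR, morphologic leukemia-free state or marrow CR achieved within 12 weeks. "Subjects will be enrolled in a cohort size of 6 with up to 36 to receive daratumumab and Venetoclax".

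The futility boundaries in Table 4 are indexed by the number "of patients evaluated for response", and the text adds: "We will apply these stopping boundaries in cohort sizes of 6". The word evaluated is not defined there or elsewhere.

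The Analysis Plan in Section 11 sets a safety population: "Data from all subjects who receive any study drug will be included in the safety analyses". For the primary endpoint it says only "We will estimate the overall response rate, along with the Bayesian 95% credible interval", with no denominator. There is no rule for a patient who dies or withdraws before a response assessment, and no replacement rule. Table 6 reports its average sample size in patients treated.

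**The concern.** Each of the five response categories is defined in Section 9 by a marrow finding. Hematologic improvement, which can be read from blood counts, is not part of the primary endpoint. Section 8 and Table 7 place the first on-treatment marrow at Cycle 2 Day 1, about week 4, and Section 8 leaves end-of-treatment assessments to the investigator's discretion. Section 7 provides for earlier exits: certain infusion reactions require withdrawal from treatment, and three consecutive missed doses can mean withdrawal from the study. Early deaths in a relapsed or refractory population add to these.

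Patients lost in Cycle 1 may therefore have no response assessment, and none of them would be a documented responder. If they are left out, the exclusion depends on outcome and always raises the response rate. Two analysts following this plan could reach different stopping decisions and different primary results. Because the study is open-label and single-center, the choice could also be made after outcomes are known.

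**Working it through.** **Inputs from Section 11.** The 15% and 25% rates: "We assume a target response rate of 25% and a response rate of 15% or lower will be considered not desirable". Priors: the response rates on the combination (P_E) and on historical treatment (P_H) "are assumed to follow a prior of Beta (0.3, 1.7) and Beta (150, 850), respectively". Rule: stop if Pr(P_E > P_H + 0.10 | data) < 0.025, with looks at 6, 12, 18, 24, 30 and 36. Table 4 boundaries at those looks: 0, 0, 1, 2, 3 and 4 responders or fewer.

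**Input not in the documents.** The share d of treated patients with no response assessment. I assume 5%, 10% and 20%, all non-responders.

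**1. Boundaries.** With r responders among n, P_E has posterior Beta(0.3 + r, 1.7 + n − r). Integrating over Beta(150, 850) for P_H gives 0.019 for 0 of 6 (stop) and 0.214 for 1 of 6 (continue). It gives 0.014 for 4 of 36 (stop) and 0.040 for 5 of 36 (continue). All Table 4 boundaries reproduce.

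**2. Table 6, every treated patient counted.** An exact binomial recursion over the six looks at a true 15% gives stopping probabilities of 0.3771 (= 0.85^6), 0, 0.0568, 0.0548, 0.0469 and 0.0395. They total 0.5752 before rounding. At a true 25% the total is 0.2119. Both match Table 6 at toxicity 0.10. If unassessed patients stay in as non-responders, these values hold for any d, because each treated patient still responds with the all-treated probability p.

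**3. Unassessed patients dropped.** The response rate among those evaluated is p/(1 − d). At p = 0.15 this is 0.15/0.95 = 15.8%, 0.15/0.90 = 16.7% and 0.15/0.80 = 18.8%. I applied the same boundaries to each sixth evaluated patient. The 36-treated column is from simulation (400,000 trials per scenario), and the 36-evaluated column is from the exact recursion at p/(1 − d).

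| Assumed d | Apparent rate, true 15% | Stop, 36 treated | Stop, enrolment to 36 evaluated |
|---|---|---|---|
| 0 | 15.0% | 0.575 | 0.575 |
| 5% | 15.8% | 0.51 | 0.54 |
| 10% | 16.7% | 0.46 | 0.49 |
| 20% | 18.8% | 0.36 | 0.40 |

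With 36 treated at a true 25%, stopping falls from 0.212 to 0.18, 0.16 and 0.11, and the apparent rate becomes 26.3%, 27.8% and 31.3%.

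**4. One look, two decisions.** Six patients are treated, none responds, and one dies in week 3. Counting all treated, 0 of 6 crosses the boundary. Counting only evaluated patients, the look waits for another patient, and if that patient responds the count is 1 of 6 and the trial continues. At a true 15%, this first look supplies 0.377 of the 0.575.

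**5. Final estimate.** Seven responders are 7/36 = 19.4% of treated patients (95% credible interval 8.5% to 33.0%). If 7 of the 36 were unassessed and dropped, they are 7/29 = 24.1% (10.6% to 39.7%), close to the 25% target.

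**The case against.** A reader might infer that the plan removes early deaths and dropouts from the denominator. It does not say so, and several features favour counting everyone. A patient who dies in week 3 has not achieved a response within 12 weeks. With 36 enrolled and no replacement, the Table 4 row at 36 can be reached only if all of them count. Table 6 fits all-treated counting. The toxicity rule also uses the word evaluated, where it may simply mean that outcome status is known. This stands: the plan is silent, and both readings are open.

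Two further inferences are not supported. Patients who progress are not clearly excluded, since a marrow is needed to document a response but not to judge that treatment has failed. Nor can bias against the historical 15% be shown, because the documents do not say which denominator produced that figure.

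The size is also conditional. The shares are assumed, and with 36 treated part of the loss comes from no longer reaching the look at 36, when enrolment is already complete. Before that look, stopping at a true 15% falls from 0.536 to about 0.50, 0.46 and 0.36. At d = 10%, about a third of the total drop is therefore the lost last look: (0.115 − 0.079)/0.115. The recomputed mean number treated, capped at 36, rises from 22.7 to 24.9 at 10% and to about 27 at 20%. The effect is modest at 5% to 10% and substantial at 20%.

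**Conclusion.** The gap is real and concerns the primary endpoint. The only efficacy count in the plan rests on an undefined term, and the final response rate has no stated denominator. The label permits a reading under which the Table 6 stopping probabilities no longer describe the trial. Under that reading, with 5% to 20% of treated patients unassessed and none a responder, the chance of stopping at a true 15% falls from 0.575 to between 0.51 and 0.36 with 36 treated, or between 0.54 and 0.40 if enrolment runs to 36 evaluated. The apparent rate rises by about 1 to 4 points, against a design margin of 10 points. This should be settled in the text before the first futility look; it does not show that the sponsor intends to exclude anyone.

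**What to change.** In Section 11:

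- Define the primary efficacy population as everyone given at least one dose of study drug.
- Count anyone without a documented response by the 12-week assessment, for any reason including death or withdrawal, as a non-responder.
- Use this denominator for both Table 4 and the final estimate, and relabel the Table 4 column as consecutively treated patients.
- Apply each boundary to consecutive cohorts of 6 once the 12-week response status of every patient in the cohort is known: response, death or withdrawal without response, or 12 weeks reached. Letting patients enter the count as their outcomes occur would over-represent early failures or early responders. At the 1 to 2 enrolments a month given in Section 5, roughly 3 to 6 patients are pending at any time.
- Report an evaluable-only rate as a sensitivity analysis.

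The boundaries and the Table 6 stopping probabilities stay as they are. The costs are a slightly less favourable reported rate than an evaluable-only one and a short wait for cohort status at each look. Section 5 already allows enrolment to continue during futility monitoring.

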To explore biomarkers predictive of response or resistance to therapy including expression of CD38 at study entry and at relapse and response rate based on CD38 expression level.

4. Hypothesis

For relapsed/refractory AML/high risk MDS and relapsed/refractory T-ALL/T-LBL, the primary hypothesis is that daratumumab in combination with venetoclax will improve the overall response rate from the historical rate of 15% by at least 10% (i.e., 25% response rate).

5. Study Design

This is a single center, Phase 2, open-label study of daratumumab and venetoclax in subjects with relapsed/refractory AML, high risk MDS and relapsed/refractory T-ALL/T-LBL. Subjects in a cohort of 6 with up to 36 subjects will be enrolled to receive daratumumab and venetoclax. Each cycle will be 4 weeks (28 days). Daratumumab will be administered at 16mg/kg weekly for the first 2 cycles (8 weeks) of treatment, followed by every 2 weeks for 4 cycles (or 16 weeks) weeks and then every 4 weeks until progression or up to 1 year of treatment whichever comes earlier. Venetoclax administration will follow the schedule indicated in package insert for administration in AML. (www.rxabbvie.com/pdf/vencluxta.pdf) Venetoclax will be administered for 21 days in each cycle and clinician will use appropriate judgement about number of days of venetoclax beyond cycle 1, based on disease status and blood counts. Tumor lysis syndrome (TLS) prophylaxis during dose ramp-up of venetoclax will be per label of venetoclax for use in AML.

On days of daratumumab dosing, the subject will receive pre-infusion medications and on the 2 days after receiving daratumumab dosing, the subject will receive post-infusion corticosteroid prophylaxis for IRR. See [Section 7C](#) and [D](#).

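### Table 6 describes a 42-patient trial, not the planned 36: two average sizes exceed the cap and every early-stopping probability is too high

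*Combined protocol and SAP*

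**What the plan says.** The maximum is given twice. Section 5 (Study Design) says "Subjects in a cohort of 6 with up to 36 subjects will be enrolled to receive daratumumab and venetoclax". Section 11 (Statistical Considerations) says "Subjects will be enrolled in a cohort size of 6 with up to 36 to receive daratumumab and Venetoclax". Tables 4 and 5 list boundaries every 6 patients and end at 36. No other maximum appears anywhere.

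The futility rule in Section 11 stops the trial if "there is less than 2.5% chance that the response rate improves over historical rate by more than 10" percentage points; "P_E and P_H are assumed to follow a prior of Beta (0.3, 1.7) and Beta (150, 850), respectively". The toxicity rule uses a Beta(0.6, 1.4) prior. It closes the trial to new patients if the posterior probability that the toxicity rate exceeds 0.30 is above 0.975. Both rules are applied in cohorts of 6.

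"Table 6. Operating characteristics for efficacy and toxicity monitoring" then gives, for 12 combinations of true response and toxicity rates, the probability of an early stop and the mean number treated. Two of the means, 37.6 and 36.6, lie above 36.

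**The concern.** A mean sample size above the maximum is impossible, so Table 6 cannot have been generated for the trial described. That also puts its probability column in doubt. If the software was run with a larger maximum, the look at 36 was counted as an interim stop. In a trial that ends at 36, it can stop nothing.

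Table 6 is the only place where the plan shows how often the design would halt an inactive or toxic combination, and after how many patients. Anyone judging the adequacy of the monitoring would rely on it.

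**Working it through.** **Inputs.** The priors and cut-offs are those in Section 11, with looks every 6 patients. Table 4 stops at responses ≤ 0, 0, 1, 2, 3, 4 and Table 5 at toxicities ≥ 5, 8, 10, 13, 15, 17, for n = 6, 12, 18, 24, 30, 36. True rates are those in Table 6. Response and toxicity are taken as independent, which is an assumption.

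**Step 1: boundaries.** After x responses in n patients, P_E ~ Beta(0.3 + x, 1.7 + n − x). Pr(P_E > P_H + 0.10) is obtained by integrating over P_H ~ Beta(150, 850). After t toxicities, P_T ~ Beta(0.6 + t, 1.4 + n − t). Every row of Tables 4 and 5 is reproduced. At n = 36, for example, 4 responses give 0.0138 (stop) and 5 give 0.0400 (continue); 17 toxicities give 0.9817 (stop) and 16 give 0.9603 (continue).

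**Step 2: recursion.** For each outcome, add a Binomial(6, p) count at each look and delete the states that stop. The remaining mass is S_R(n) for response and S_T(n) for toxicity, and S(n) = S_R(n) × S_T(n), with S(0) = 1. Then:
- P(stopped by n) = 1 − S(n)
- E[N] = 6 × [S(0) + S(6) + … + S(max − 6)]

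**Step 3: two rows in full.**

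| Response / toxicity | S(0) | S(6) | S(12) | S(18) | S(24) | S(30) | S(36) |
|---|---|---|---|---|---|---|---|
| 0.30 / 0.10 | 1 | 0.8823 | 0.8823 | 0.8781 | 0.8751 | 0.8731 | 0.8718 |
| 0.30 / 0.50 | 1 | 0.7858 | 0.6814 | 0.4947 | 0.4265 | 0.3187 | 0.2268 |

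Reproducing the plan's figures (maximum 42, stops at 6 to 36):
- 0.30 / 0.10: 1 − 0.8718 = 0.1282, and 6 × 6.2627 = 37.58. Printed: 0.1282 and 37.6.
- 0.30 / 0.50: 1 − 0.2268 = 0.7732, and 6 × 3.9339 = 23.60. Printed: 0.7732 and 23.6.

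As planned (maximum 36, early stops at 6 to 30):
- 0.30 / 0.10: 1 − 0.8731 = 0.1269, and 6 × 5.3909 = 32.3.
- 0.30 / 0.50: 1 − 0.3187 = 0.6813, and 6 × 3.7071 = 22.2.

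**Step 4: all rows.** With a maximum of 42, all 12 probabilities agree to 4 decimals and all 12 averages agree within rounding (largest difference 0.05). With a maximum of 36:

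| Response | Toxicity | Printed P / N | 36-patient P / N | Excess in P (points) | Excess in N |
|---|---|---|---|---|---|
| 0.15 | 0.10 | 0.5752 / 25.3 | 0.5357 / 22.7 | 4.0 | 2.6 |
| 0.15 | 0.30 | 0.5959 / 24.7 | 0.5548 / 22.3 | 4.1 | 2.4 |
| 0.15 | 0.40 | 0.7049 / 22.3 | 0.6484 / 20.5 | 5.7 | 1.8 |
| 0.15 | 0.50 | 0.8895 / 17.3 | 0.8305 / 16.6 | 5.9 | 0.7 |
| 0.25 | 0.10 | 0.2119 / 35.0 | 0.2064 / 30.3 | 0.6 | 4.7 |
| 0.25 | 0.30 | 0.2504 / 34.1 | 0.2390 / 29.6 | 1.1 | 4.5 |
| 0.25 | 0.40 | 0.4526 / 30.2 | 0.3990 / 26.9 | 5.4 | 3.3 |
| 0.25 | 0.50 | 0.7950 / 22.3 | 0.7103 / 21.0 | 8.5 | 1.3 |
| 0.30 | 0.10 | 0.1282 / 37.6 | 0.1269 / 32.3 | 0.1 | 5.3 |
| 0.30 | 0.30 | 0.1708 / 36.6 | 0.1628 / 31.6 | 0.8 | 5.0 |
| 0.30 | 0.40 | 0.3945 / 32.3 | 0.3389 / 28.6 | 5.6 | 3.7 |
| 0.30 | 0.50 | 0.7732 / 23.6 | 0.6813 / 22.2 | 9.2 | 1.4 |

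**Step 5: a check by hand.** The 42- and 36-patient averages differ by 6 × S(36), which is 6 × (1 − printed P). For 0.30 / 0.50 this is 6 × 0.2268 = 1.36, and 23.6 − 1.36 = 22.24, as in Step 3.

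**Step 6: other explanations, tested on the 0.30 / 0.10 row.**
- Maximum 36 with the n = 36 look counted: the probability matches (0.1282), the average does not (32.3).
- Maximum 40: the average is 32.345 + 4 × 0.8718 = 35.8, not 37.6.
- Maximum 42 with a stop at 42 also counted: the probability becomes 0.1290.
- Maximum 48: 0.1290 and 42.8.

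**The case against.** The best defence concerns the probability column. The printed values equal the chance of crossing any Table 4 or Table 5 boundary up to and including n = 36, whether the maximum is 36 or 42. Relabelled in that way they would be correct. But the column is headed as early stopping, and the toxicity rule acts by closing enrolment; after the 36th of 36 patients there is none left to close. Relabelling also does nothing for the averages, all 12 of which are too high.

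Four further points stand as limits:
- The probability gaps are uneven. They are only 0.1 to 1.1 points where response is 0.25 or 0.30 and toxicity 0.10 or 0.30.
- A lower true average means fewer patients exposed, not more, so the averages do not err in the design's favour on exposure.
- The replacement values assume immediate evaluation at each look. Section 5 does not hold enrolment for futility and expects 1 to 2 patients a month, while response is assessed over 12 weeks. Roughly 3 to 6 patients could enter while a look is pending. The values are comparable with Table 6, but they are not a forecast of conduct.
- Tables 4 and 5, not Table 6, govern stopping, and they are correct.

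**Conclusion.** The concern holds. The conflict between a cap of 36 and averages of 37.6 and 36.6 is explicit and needs no modelling. The 42-patient basis is an inference, since the documents never mention 42, but agreement on all 24 entries leaves little room for another explanation.

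For the planned 36 patients, the chance of an early stop is overstated in every scenario. The excess is 5.9 to 9.2 points at 50% toxicity, 5.4 to 5.7 at 40%, and about 4 at response 0.15 with lower toxicity. This rests on independence of response and toxicity, immediate evaluation, and not counting a crossing at n = 36 as early. The first two assumptions also reproduce Table 6 itself. A core design table with impossible entries must be corrected, although no boundary or decision during the trial changes.

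**What to change.** Confirm the intended maximum. If it is 36, re-run the design software with that maximum and looks at 6, 12, 18, 24 and 30, and replace Table 6; the 36-patient column in Step 4 shows the values to expect. Keep the n = 36 rows of Tables 4 and 5 only if they are relabelled as an end-of-trial classification; otherwise remove them as stopping looks. State under Table 6 the maximum, the looks counted as early stops, and the independence assumption. If 42 was in fact intended, Sections 5 and 11 and both boundary tables need reconciling with it instead.

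With 36 confirmed, the cost is one software run and a table replacement. The stated early-stopping probabilities become less favourable. Boundaries and patient numbers stay the same.
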